8.5.3 Treatment of Adverse Events

Any medication administered for the treatment of an SAE/pIMD should be recorded in the Expedited Adverse Events report of the participant's eCRF screen.

8.5.4 Follow-up of AEs and SAEs

After the initial AE/SAE report, the investigator is required to proactively follow each participant at subsequent visits/contacts. All AEs (Section 10.5) will be followed until resolution, stabilization, the event is otherwise explained, or the participant is lost to follow-up (as defined in Section 7.3). Further information on follow-up procedures is provided in Section 10.5.

8.5.5 Regulatory Reporting Requirements for SAEs and Other Events

Prompt notification by the investigator to the Sponsor of an SAE or pIMD is essential so that legal obligations and ethical responsibilities toward the safety of participants and the safety of a study intervention under clinical investigation are met.

The Sponsor has a legal responsibility to notify both the local regulatory authority and other regulatory agencies about the safety of a study intervention under clinical investigation. The Sponsor will comply with country-specific regulatory requirements relating to safety reporting to the regulatory authority, IRBs/IECs, and investigators.

For SAEs and pIMDs, the investigator must always provide an assessment of causality at the time of the initial report, as defined in the Section 10.5.3.

An investigator who receives an investigator safety report describing an SAE or other specific safety information (e.g., summary or listing of SAEs) from the Sponsor will review and then file it along with the IB and will notify the IRB/IEC, if appropriate according to local requirements.

Table 8 Timeframes for Submitting SAE, Pregnancy, pIMDs to IQVIA

Type of event	Initial reports		Follow-up of relevant information on a previous report	
	Timeframe	Documents	Timeframe	Documents
SAEs	24 hours* ‡‡	Electronic [‡] AEs Report	24 hours*	Electronic [‡] AEs Report
Pregnancies	24 hours*	Electronic pregnancy report	24 hours *	Electronic pregnancy report
pIMDs (whether serious or non-serious)	24 hours** ‡‡	Electronic [‡] AEs Report	24 hours*	Electronic [‡] AEs Report

Abbreviation: AE=adverse event; SAE=serious adverse event; pIMD=potential immune-mediated disease.

* Timeframe allowed after receipt or awareness of the information by the investigator/site staff.

**Timeframe allowed once the investigator determines that the event meets the protocol definition of a pIMD.

[‡] Paper AEs report may be submitted in the case that the electronic system is not functioning. The paper report will be dated and signed by the investigator (or designee). For each SAE/pIMD, the investigator(s) must document in the medical notes that they have reviewed the SAE/pIMD and have provided an assessment of causality.

‡‡ The investigator will be required to confirm review of the SAE/pIMD causality by ticking the ‘reviewed’ box in the electronic Expedited Adverse Events Report within 72 hours of submission of the SAE/pIMD.

8.5.6 Pregnancy

Details of all pregnancies in study participants will be collected after the start of study intervention and until the outcome of the pregnancy is known. Female participants who become pregnant after the first study intervention dose must not receive the second dose of the study intervention but may continue other study procedures at the discretion of the investigator.

If a pregnancy is reported, the investigator will record pregnancy information on the appropriate form and submit it to the Sponsor or designee within 24 hours of learning of the participant's pregnancy and should follow the procedures outlined in Section [10.5.3](#)

While pregnancy itself is not considered to be an AE or SAE, any pregnancy complication or elective termination of a pregnancy for medical reasons will be reported as an AE or SAE.

If the outcome of the pregnancy meets the criteria for immediate classification as an SAE (i.e., spontaneous abortion, stillbirth, neonatal death, or congenital anomaly [including if found in an aborted fetus, stillbirth, or neonatal death]) the investigator will report according to the SAE reporting procedures described in Section [10.5.5](#).

The participant will be followed to determine the outcome of the pregnancy. The investigator will collect follow-up information on the participant and the neonate and the information will be forwarded to the Sponsor or designee.

Any post-study pregnancy-related SAE considered reasonably related to the study intervention by the investigator will be reported to the Sponsor as described in Section [8.5.5](#). While the investigator is not obligated to actively seek this information in former study participants, he or she may learn of an SAE through spontaneous reporting.

8.5.7 Adverse Events of Special Interest

8.5.7.1 Potential Immune-Mediated Diseases

Potential immune-mediated diseases are a subset of AESIs that include autoimmune diseases and other inflammatory and/or neurologic disorders of interest which may or may not have an autoimmune etiology. Adverse events that need to be recorded and reported as pIMDs include those listed in [Table 16](#) and must be reported in an expedited manner regardless of causality, seriousness, or medical opinion on etiology.

The investigator(s) must exercise their medical/scientific judgment to determine whether other diseases have an autoimmune origin (i.e., pathophysiology involving systemic or organ-specific pathogenic autoantibodies) and should also be recorded as a pIMD. In addition, the investigator should categorize each pIMD as a new onset condition (if it started following vaccination) in the eCRF.

8.5.8 Participant Card

The investigator (or designee) must provide the participant/participant's caregiver(s) with a "participant card" containing information about the clinical study. The participant/participant's caregiver(s) must be instructed to always keep the participant card in their possession for the duration of the study. In an emergency, this card serves to inform the responsible attending physician/caregiver/family member that the participant is in a clinical study and that relevant information may be obtained by contacting the investigator(s) or their back-up.

8.6 Pharmacokinetics

Pharmacokinetic parameters are not evaluated in this study.

8.7 Pharmacodynamics

Pharmacodynamic parameters are not evaluated in this study.

8.8 Genetics

Genetics are not evaluated in this study.

8.9 Biomarkers

Biomarkers are not evaluated in this study.

8.10 Immunogenicity Assessments

Immunogenicity Assessments are described in Section [8.2](#).

8.11 Health Economics

Health economics parameters are not evaluated in this study.

9.0 STATISTICAL CONSIDERATIONS

The Statistical Analysis Plan (SAP) will be finalized prior to first subject first visit (FSFV).

9.1 Statistical Hypotheses

The null hypotheses for vaccine-homologous HI titer at Day 43 in 18 to 64 years age or in 65 years of age or above) are:

for 18 to 64 years of age: $H_0: \text{seroprotection rate (SPR)} < 70\%$

for 65 years of age or above: $H_0: \text{SPR} < 60\%$

Null hypotheses will be assessed according to a hierarchical order of study groups as given below.

1. 7.5 mcg antigen + AS03A
2. 7.5 mcg antigen + AS03B
3. 3.75 mcg antigen + AS03A
4. 3.75 mcg antigen + AS03B

No multiplicity adjustment is required as the hypothesis for each study group will be tested if the success criteria will be met for the previous group in the hierarchy. Accordingly, a nominal type I error of 2.5% will be used for each dose group and the objective will be met for one dose group if all 2 null hypotheses are rejected simultaneously.

Criteria for success to be met simultaneously for a study group:

- The lower limit (LL) of the 95% confidence interval (CI) for the SPR meets or exceeds 70% for adults of 18 to 64 years of age.
- The LL of the 95% CI for the SPR meets or exceeds 60% for adults ≥ 65 years of age.

9.2 Sample Size Determination

A total of 520 participants are planned to be enrolled, with 65 participants per age subgroup in each of the 4 dose groups.

A non-evaluable rate of 23% and 30% in 18 to 64 years of age and ≥ 65 years of age groups, respectively yield an approximate sample size of 95 evaluable participants per dose group (i.e., 50 participants between 18 to 64 years of age and 45 participants above 65 years of age in each dose group), giving 77.8% overall power to fulfill the 2 SPR immunogenicity criteria in any in the first group that is 7.5 mcg antigen + AS03A. This assumes that the SPR are truly 20% higher than the critical value (namely 90% for participants 18 to 64 years of age and 80% for participants ≥ 65 years of age, respectively).

The statistical power in 7.5 mcg antigen + AS03A group will be 91.4% if the SPR is assumed as 85% in ≥ 65 years of age.

9.3 Analysis Sets

Table 9 Analysis Sets

Analysis Set	Description	Analyses Evaluated
Screened	All participants who were screened for eligibility.	Study Population
Enrolled (ENR)	All participants who were randomized, received study intervention or had immunogenicity blood sample.	Study Population
Exposed Set (ES)	Participants who received a study intervention. Participants will be analyzed according to the study intervention administered at dose 1.	Safety (unsolicited AE, number of participants with changes in laboratory toxicity grading from baseline, SAE, pIMD, MAE)
Diary Set (DS)	Participants who received a study intervention and provided information on solicited AEs. Participants will be analyzed according to the study intervention administered at dose 1.	Solicited AE
Per Protocol Set (PPS)	
All eligible participants who received the 2 doses of study intervention as per protocol, had Day 1 and Day 43 post dose anti-HI immunogenicity results as per blood draw interval at Day 43.
 
In addition, participant data at a specific blood draw visit will be excluded from the PPS when:
 
 • Results from a serological blood sample deviated from blood draw intervals (refer to Table 2) • Results from a serological blood sample occurred after intercurrent conditions that may interfere with immunogenicity (i.e., immunosuppressive, immunodeficient conditions, or malignancy) or after a prohibited concomitant medication/vaccination 
The analysis will be done according to the treatment that participants received at Visit 1.
	
Efficacy
 
The PPS will be used for the immunogenicity analyses.

9.3.1 Criteria for Elimination from Analysis

All conditions leading to full or partial data elimination of a participant for the per protocol set (PPS) analysis will be classified as major protocol deviations. These conditions are already mentioned in the PPS definition and will be further detailed in the SAP and the Study Deviation Rules document which will be finalized prior to the interim analysis defined in Section 9.5.

Key major deviations include, but are not limited to, the following:

- Participants enrolled who did not meet eligibility criteria
- Participants incorrectly vaccinated
- Participants who did not receive study vaccinations as planned in protocol
- Participants who did not have serological blood draws as planned in protocol
- Participants with a blood draw outside of allowed time window
- Participants with a vaccination done outside of allowed time window. These key major deviations will be assessed based on the data collected in the eCRFs.
- Occurrence of immunosuppressive or immunodeficient conditions before a blood draw visit.

9.4 Statistical Analyses

The SAP will be developed and finalized before FSFV and will include a more technical and detailed description of the statistical analyses including the supportive analyses and demographic summaries. This section is a summary of the planned statistical analyses of the primary and secondary endpoints.

9.4.1 General Considerations

All analyses will be provided separately for each age subgroup.

Derived and transformed data:

- Immunogenicity at a visit (Note: The lower limit of quantitation (LLOQ) is defined by the laboratory before the analysis and will be specified in the clinical study report).
 - A seronegative participant is a participant whose titer is below the LLOQ.
 - A seropositive participant is a participant whose titer is greater than or equal to the LLOQ.
 - Seroprotection is defined as an HI titer $\geq 1:40$.
 - SPR is defined as the percentage of participants with an HI titer $\geq 1:40$.
 - HI seroconversion is defined as a post-vaccination titer $\geq 1:40$ in the serum of participants with pre-vaccination titer below 1:10 or as a ≥ 4 -fold rise in post-vaccination HI titer with pre-vaccination titer $\geq 1:10$.

- SCR is defined as the percentage of participants who seroconvert post-vaccination.
- MN vaccine response (VR) is defined as titer $\geq 4 \times$ LLOQ for participants with pre-vaccination titer below LLOQ or as a ≥ 4 -fold increase in MN titer for participants with pre-vaccination titer \geq LLOQ.
- Vaccine response rate (VRR) is defined as the percentage of participants with vaccine response.
- Geometric Mean Titer (GMT) calculations are performed by taking the anti-log of the mean of the log concentration/titer transformations. Values for the concentrations/titers below the LLOQ will be assigned half the LLOQ for the purpose of GMT computation.
- Handling of missing data: for a given participant and a given immunogenicity measurement, missing or non-evaluable measurements will not be replaced.
- The primary and secondary HI immunogenicity analyses will be based on the PPS.
- The MN immunogenicity analyses will be based on the PPS.

- Reactogenicity and Safety – Handling of missing data: For safety analyses, participants who missed reporting symptoms (solicited or unsolicited) or concomitant medications will not be imputed. Therefore, the analysis of the solicited symptoms based on the DS will include only participants/doses with documented safety data (i.e., symptom screen/sheet completed). Further details on the handling of missing data will be described in the SAP.

9.4.2 Participants Disposition

Participant disposition will be summarized for the enrolled set across groups and for ES for each study group and overall. The summary will include the number of participants in each analysis set defined in Section 9.3, the number and percentage of participants who received any and each study vaccination, the number and percentage of participants who completed the study and/or the primary reason for withdrawal from the study, the number and percentage of participants who completed the study vaccinations and/or the primary reason for withdrawal of study vaccination.

The number and percentage of participants who were screen failures and the major reason for screen failure will be summarized for the Screened set as overall.

Major deviations will be summarized for the ES for each study group and overall.

The reason for elimination from the DS and from the PPS will also be summarized at each vaccination and post-vaccination blood draw respectively.

Listings will be provided for disposition data and deviation data based on the enrolled set.

9.4.3 Primary Endpoint(s)/Estimand(s) Analysis

9.4.3.1 Immunogenicity

Primary immunogenicity analyses will be based on the PPS.

GMTs and associated 95% CI will be calculated for each study group for vaccine-homologous H5N8 HI titer at Day 43.

GMFR increase at Day 43, compared to pre-vaccination and associated 95% CI will be calculated for each study group for vaccine-homologous H5N8 HI titer at Day 43. The GMT and GMFR CIs will be derived from an Analysis of Covariance (ANCOVA) model on log-transformed titer. The model will include the dose group effect (i.e., 4 dose groups), as a fixed effect and the log-transformed titer pre-dose 1 (Day 1) as a covariate.

SPR at Day 43 will be calculated for each study group for vaccine-homologous H5N8 HI titer along with Clopper-Pearson exact two-sided 98.75% CIs.

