9.5.2 Statistical Consideration for Interim Analysis

Since the primary endpoints for the study will be complete by the Day 43 visit (collection past Day 43 includes only assessments for SAEs, pIMDs, MAEs, and immunogenicity at 6 months post dose 2), no statistical consideration for multiplicity will be given to account for changes in the results reported at the interim analysis compared to the final analysis. For the primary immunogenicity analysis, which will be reported at Day 43 the overall type I error rate is fixed at 2.5% and a Bonferroni adjustment will be applied to allow simultaneous multiple comparisons of each antigen/adjuvant group leading to 0.625% nominal type I error. For the primary safety analyses no adjustment for multiple comparisons will be made in each antigen/adjuvant group.

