### 15.1.3. Primary Analysis of Primary Immunogenicity Variables

The primary immunogenicity endpoints will be analyzed, for the PPS, as follows:

- GMTs, with 95% CIs, will be calculated for each study intervention group for vaccine-homologous H5N8 HI titer at Day 43.
- GMFR at Day 43, compared to pre-vaccination, will be calculated for each study intervention group for vaccine-homologous H5N8 HI titer at Day 43 with 95% CIs.
- The CIs for GMT and GMFR and will be derived from an ANCOVA model on log-transformed titer. This model will include the dose group effect (i.e., 4 dose groups) as a fixed effect and the log-transformed titer pre-dose 1 (Day 1) as a covariate.
- HI SP, defined as meeting vaccine-homologous H5N8 HI titer  $\geq 1:40$ , will be analyzed by reporting SPR.

---

Document: \\ieedc-vnasc01\BIOSdata\GSK\H5N8(Flu)\HAB99808\Biostatistics\Documentation\SAP\SAP\SAP v5.0\GSK H5N8-219833\_SAP\_v5.0\_19AUG2024.docx

Author: PPD Version Number: 5.0  
Version Date: 19AUG2024

Template No.: CS\_TP\_BS016 Revision 7

Reference: CS\_WI\_BS005

Effective Date: 01Nov2021

SPR is defined as the percentage of participants who meet the SP definition and will be reported at Day 43 with Clopper-Pearson exact two-sided 95% CIs for each study intervention group.

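### The protocol carries two decision rules for the primary seroprotection hypotheses: a fixed sequence with 95% CIs, and Bonferroni with 98.75% CIs. The stated 77.8% power holds only under the first.

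*Protocol*

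**What the plan says.** **The fixed-sequence rule.** Protocol 9.1 states that "Null hypotheses will be assessed according to a hierarchical order of study groups as given below", beginning with 7.5 mcg + AS03A and ending with 3.75 mcg + AS03B. It adds that "a nominal type I error of 2.5% will be used for each dose group", and a group is tested only if the one before it succeeded. A group succeeds only if both age criteria are met:

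- 18 to 64 years: "The lower limit (LL) of the 95% confidence interval (CI) for the SPR meets or exceeds 70" per cent.
- 65 years and over: "The LL of the 95% CI for the SPR meets or exceeds 60% for adults" in that stratum.

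SAP 2.3 and 7.4 repeat this rule. SAP 15.1.3 gives the matching interval: the Day 43 rate "will be reported at Day 43 with Clopper-Pearson exact two-sided 95% CIs for each study intervention group".

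**The Bonferroni rule.** Protocol 9.4.3.1 is the section that specifies the primary immunogenicity analysis. It calculates the Day 43 seroprotection rate (SPR) "along with Clopper-Pearson exact two-sided 98.75% CIs" and gives no 95% interval for it. Protocol 9.5.2 says of the same analysis that "a Bonferroni adjustment will be applied to allow simultaneous multiple comparisons of each antigen/adjuvant group leading to 0.625% nominal type I error".

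**What the SAP declares.** The SAP is based on protocol amendment 3.0 and follows the 95% rule throughout. Its section 3.3, on changes to the analysis from the protocol, reports none.

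**The concern.** These are the only formal success criteria in the trial, and the protocol gives two versions of them. They differ in two ways.

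- **Threshold.** The same titers can pass the 95% limit and fail the 98.75% limit.
- **Structure.** Under 9.1, failure of 7.5 mcg + AS03A ends testing. Under 9.5.2, all four groups are compared at once, so a later group could succeed after the first has failed.

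Either rule used alone keeps the familywise error at 2.5%. An unresolved choice between them does not guarantee that. If success could be claimed under whichever rule turned out favourable, the nominal bound would be 2.5% + 3 × 0.625% = 4.375%: the first true null in the sequence at 2.5%, plus up to three others at 0.625%. Until the text is reconciled, a claim of 2.5% error control is open to challenge.

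**Working it through.** **Inputs**

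- Null SPR: 70% (18 to 64 years) and 60% (65 and over), from protocol 9.1.
- Evaluable numbers: "50 participants between 18 to 64 years of age and 45 participants above 65 years of age in each dose group" (protocol 9.2). Check: 65 × 0.77 = 50.05 and 65 × 0.70 = 45.5.
- Assumed true SPR: 90% and 80%, with 85% in the older stratum as the alternative (protocol 9.2).
- One-sided level per criterion: 0.025 for a 95% CI, and 0.025/4 = 0.00625 for a 98.75% CI, since 1 − 2 × 0.00625 = 0.9875.

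**Formulas**

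- Clopper-Pearson lower limit for x of n: the α quantile of Beta(x, n − x + 1).
- Critical count r: the smallest x whose lower limit reaches the null value.
- Stratum power: P(X ≥ r) for X binomial with n and the true SPR.
- Joint power for a dose group: the product of the two stratum powers, because the strata contain different participants.

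**Lower limits near the cut-offs**

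| Result | 95% CI | 98.75% CI | Null |
|---|---|---|---|
| 41/50 | 68.6% | 64.8% | 70% |
| 42/50 | 70.9% | 67.2% | 70% |
| 43/50 | 73.3% | 69.6% | 70% |
| 44/50 | 75.7% | 72.1% | 70% |
| 33/45 | 58.1% | 54.0% | 60% |
| 34/45 | 60.5% | 56.4% | 60% |
| 35/45 | 62.9% | 58.9% | 60% |
| 36/45 | 65.4% | 61.4% | 60% |

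The critical counts are therefore 42/50 and 34/45 at 95%, and 44/50 and 36/45 at 98.75%.

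**Reproducing the stated power (95% rule)**

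- True SPR 90% and 80%: 0.9421 × 0.8259 = 0.7781. Stated: 77.8%.
- True SPR 90% and 85%: 0.9421 × 0.9698 = 0.9137 (from unrounded factors). Stated: 91.4%.

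**Same inputs, 98.75% rule**

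- True SPR 90% and 80%: 0.7702 × 0.5880 = 0.4529, or 45.3%.
- True SPR 90% and 85%: 0.7702 × 0.8726 = 0.6721, or 67.2%.

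Other interval methods do not rescue 77.8% at the stricter level. At 98.75%, Wilson gives 45.3%, a normal approximation 50.2% and Wald 67.9%.

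**Chance that the rules disagree.** Any result that passes at 98.75% also passes at 95%. The probability that the first dose group passes one and fails the other is therefore the difference in joint power:

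- 90% and 80%: 0.7781 − 0.4529 = 0.3252, about 32.5%.
- 90% and 85%: 0.9137 − 0.6721 = 0.2416, about 24.2%.

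**Where the second rule comes from.** The protocol's summary of changes for amendment 3.0 records that 9.1 moved from Bonferroni with 98.75% intervals to the hierarchy with 95%, and that 9.2 previously gave 73.5% power with 60 evaluable per stratum. At 98.75% with 60 and 60, the critical counts are 51 and 46 and the joint power is 0.9269 × 0.7935 = 0.7355, which matches that superseded figure. So 9.4.3.1 and 9.5.2 read as the earlier design left in place when 9.1 and 9.2 were changed.

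**The case against.** The best reply is that the intended rule is clear. Section 9.1 alone lists criteria for success, and they name the 95% interval. Section 9.4.3.1 attaches no threshold to its 98.75% interval, and 9.4 calls itself a summary, with detail left to the SAP. The SAP follows 9.1 consistently, and its modification history (version 3.0, 11 January 2024) records the SPR intervals going from 98.75% to 95%. On this reading two passages are stale and the rule is not in doubt.

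Much of that stands: the fixed sequence with 95% intervals is very probably what is meant, and the written record weakens any suggestion of a choice made after the results. It does not remove the conflict. Section 9.5.2 expressly assigns 0.625% to the primary immunogenicity analysis, 9.4.3.1 supplies the matching interval, and no clause says which section prevails. The SAP history records changes between SAP versions; the place to declare departures from the protocol is 3.3, which declares none.

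Two qualifications on size are fair:

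- A result of 42–43/50 or 34–35/45 changes a group's verdict only if the other stratum meets its own 95% cut-off. Otherwise the group fails under both rules.
- The 45.3% is power for one dose group. Under Bonferroni any of four groups may succeed. If all four shared the same true rates and were independent (an assumption), the chance that at least one succeeds would be 1 − (1 − 0.4529)⁴ = 91%. The per-group comparison measures how strict each rule is, not the trial's overall chance of a success.

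**Conclusion.** The concern holds and must be fixed. The current protocol contains two incompatible pass/fail rules for its primary hypotheses, and the SAP follows one without declaring that it departs from 9.4.3.1 and 9.5.2. The stated 77.8% and 91.4% are correct for the 95% rule; under the 98.75% rule the same group has 45.3% and 67.2%. The pass marks differ by two responders in each stratum, and the first dose group has about a 32.5% chance of a result on which the rules disagree (24.2% at the more favourable SPR).

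These figures assume exactly 50 and 45 evaluable participants, the protocol's true rates, and Clopper-Pearson limits. The cut-offs will move with the actual per-protocol numbers, but the conflict between the sections does not depend on them. The documents do not say when HI results became available or were unblinded, so a post hoc choice of rule can be neither shown nor excluded.

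**What to change.** Keep the rule in 9.1, which the sample size and the SAP already use.

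1. In protocol 9.4.3.1, change the interval for the Day 43 SPR from 98.75% to 95%.
2. In protocol 9.5.2, replace the Bonferroni sentence with the fixed-sequence procedure of 9.1: one-sided 2.5% at each step, both age criteria required, testing stops at the first group that fails.
3. If the protocol will not be amended again, replace the statement in SAP 3.3 with a short paragraph naming both departures, dated before the HI data are unblinded. If unblinding has already happened, the paragraph should say so and state when the 95% fixed-sequence rule was adopted, citing the dated amendment and SAP version.

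If the sponsor wants Bonferroni after all, then 9.1, 9.2 and the SAP must change instead, and the per-group power must be restated as about 45%.

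The recommended change costs two sentences in the protocol or one paragraph in the SAP, with no additional participants and no new analysis.
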